#### 7.5.2 Patient-Level Analyses of Diagnostics by [Ga]-NeoBOMB1 *in vivo* Imaging versus Histology

At patient level, patients with at least one positive lesion on [Ga]-NeoBOMB1-PET versus those without positive lesions on [Ga]-NeoBOMB1-PET will be cross-tabulated with positive or negative results of GRPR expression by histological analyses. The cross-tabulations will be done for overall results and for each tumor type. Sensitivity and specificity values will be calculated for each two-way contingency table displayed. The sensitivity and specificity will be calculated as follows:

- Sensitivity = 100% x True positive / (True positive + False negative)
- Specificity = 100% x True negative / (True negative + False positive)

#### 7.5.3 Relationship between [Ga]-NeoBOMB1 Diagnostics and GRPR Expression Level

Histological assessment of GRPR expression and the diagnostic performance of [Ga]-NeoBOMB1 may be compared. The scatter plot of GRPR expression versus *in vivo* imaging

sensitivity (proportion of conventional imaging lesions also detected by [Ga]-NeoBOMB1 PET imaging) on patient level will be generated, and the strength of association will be properly assessed. If the assumption of linear relationship seems adequate, the Pearson's correlation coefficient will be computed. Otherwise, Spearman's rank-order correlation coefficient will be derived.

The correlative analyses between [Ga]-NeoBOMB1 diagnostic performance and GRPR expression level will be conducted for each tumor type and for all available data.

#### 8 ANALYSIS OF SAFETY

Safety analyses will be summarized based on FAS and split by tumor type and in total unless otherwise specified.

#### 8.1 Adverse Events

AEs will be coded using MedDRA version available at the time (updated biannually).

Treatment-emergent adverse events (TEAEs) are defined as AEs that start on or after the initiation of IMP administration.

Intensity of all adverse events will be graded according to the Toxicity Grading Scale in vaccine clinical trials. Adverse events not listed in the Toxicity Grading Scale in vaccine clinical trials should be graded as guided in study protocol.

An overview of AEs will be provided which summarizes subject incidence of the following information:

- Any TEAEs,
- Drug-related TEAEs,
- Grade 3/4/5 TEAEs,
- Drug-related grade 3/4/5 TEAEs,
- Deaths due to AEs,
- Treatment-emergent SAEs,
- Drug-related treatment-emergent SAEs,
- Dose interruption due to TEAEs, and
- Dose interruption due to drug-related TEAEs.

The number and percentage of subjects with TEAEs will be summarized by SOC and PT. Drugrelated TEAEs, treatment-emergent SAEs, drug-related treatment-emergent SAEs, TEAEs leading to dose interruption of study drug, and drug-related TEAEs leading to dose interruption of study drug will be summarized in the same manner. For these summaries, subjects with multiple adverse events will be counted only once per SOC and PT. Note that drug-related AEs include the AEs which either definitely, probably, or possibly related to study drug.

Summaries will be provided by the worst toxicity grade, SOC, and PT for the number and percentage of subjects with TEAEs and drug-related TEAEs. For these summaries, subjects with multiple adverse events will be counted only once by the worst toxicity grade within each SOC and PT.

Data listings will be provided for SAEs, grade 3/4/5 AEs, AEs leading to dose interruption, Hypersensitivity (SMQ) AEs, and AEs leading to death. A by-subject AE data listing including, but not limited to, verbatim, PT, SOC, toxicity grade, action taken, outcome, and relationship to study drug will be provided.

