# 4.2 Schedule of assessments

### 4.2.1 Screening period (Visit 0, days –28 to – 1)

The screening examinations must be performed between 1 and 28 days before being enrolled in the study (i.e. administration of [Ga]-NeoBOMB1). Only subjects fulfilling all the inclusion and none of the exclusion criteria will be accepted in the study.

The following study screening assessments are to be completed within 1 to 28 days prior to study entry:

- Signed and dated informed consent
- Reviewed inclusion and exclusion criteria
- Demographic data: age and sex
- Medical history: relevant prior or persisting illnesses including known allergies, prior anaphylactic reactions, metabolic disorders, vascular disorders, hypertension, history of stroke or myocardial infarction, other known malignancies, prior treatment
- Concomitant medication
- Physical examination: weight, auscultation of lungs and heart, oral inspection, abdominal palpation
- Vital signs: blood pressure, heart rate
- Routine ECG including frequency-corrected QT-time
- Haematology, Blood chemistry, Coagulation parameters, Urinalysis
- Urine dipstick pregnancy test (in women of childbearing potential)

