# 6.1 Adverse Events (AEs)

An adverse event (AE) is defined as any untoward medical occurrence in the form of signs, symptoms, abnormal laboratory findings, or diseases that emerges or worsens relative to baseline during a clinical study with an investigational product, regardless of causal relationship and even if no investigational product has been administered.

Adverse events include:

- Worsening or increase in frequency or intensity of a pre-existing disease or medical condition
- Abnormal laboratory tests

Adverse events do not include:

- Pre-planned interventions/hospitalizations
- Medical or surgical procedures, e.g. surgery, endoscopy, tooth extraction, transfusion. However, the event leading to the procedure is an AE. If this event is serious, the procedure must be described in the SAE narrative.
- Pre-existing disease or medical condition that does not worsen.
- Diagnosis of progressive disease i.e. increase in tumour load or newly identified metastasis/complication during routine diagnostic CT.
- Overdose of either study drug or concomitant medication without any signs or symptoms that should be considered only as a specific situation.

All AEs will be reported and recorded from the signature of the ICF.

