# 6.8 Reporting procedures for AEs

A special section is designated to adverse events in the CRF where the following details must be entered:

- Type of adverse event (diagnosis or syndrome; if not known signs or symptoms) and brief description (including context of occurrence)
- Start (date)
- End (date)
- Severity (mild, moderate, severe, life-threatening/disabling, death)
- Serious (no / yes)
- Outcome (resolved, ongoing, ongoing improved, ongoing worsening) and recovery date
- Action taken (none, study medication dose reduced, study medication interrupted, study medication discontinued, medication therapy, surgical procedure, hospitalization, other)
- Relation to study drug (possibly, probably or definitely related or unlikely, probably not related or definitely not related)
- Treatment date with the IMP (in order to estimate the time to onset)

• Patients relevant medical history and/or concomitant treatments that may provide alternative explanation regarding the AEs occurrence.

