# 6.11 Adverse Event Reporting Period

All AEs will be reported and recorded from the signature of the ICF.

Investigators will seek information on AEs at each patient contact throughout the trial. All AEs, whether reported by the patient or noted by study personnel, will be recorded in the patient's medical record and on the Adverse Event part of the application day Case Report Form (CRF).

After informed consent has been obtained all AEs and SAEs regardless of relationship to the study drug will be reported until FU3 or until the event has resolved to baseline grade or better, the event is assessed as stable by the investigator, the patient is lost to follow-up, or the patient withdraws consent.

After FU3, investigators should report any deaths, SAEs, or other AEs of concern that are believed to be related to prior treatment with the study drug.

Any Serious Adverse Event (SAE) that is ongoing at the time of FU3 should be followed-up until resolved.

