#### 5.2 Baseline Definition

Baseline value for any given variable is defined as the last assessment obtained prior to the initiation of the [Ga]-NeoBOMB1 administration.

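### SAP 8.1 defines treatment-emergent AEs by onset date alone, so an AE that arises in screening and worsens after injection can be missing from every TEAE table

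*SAP*

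**What the plan says.** The SAP definition, in section 8.1, rests on onset: "Treatment-emergent adverse events (TEAEs) are defined as AEs that start on or after the initiation of IMP administration". Nothing is added for an event already present at injection that then gets worse.

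The protocol's notion of an AE is wider. Section 6.1 covers "diseases that emerges or worsens relative to baseline during a clinical study with an investigational product", and its list of what counts includes "Worsening or increase in frequency or intensity of a pre-existing disease or medical condition". Recording begins before dosing. Section 6.11 says "All AEs will be reported and recorded from the signature of the ICF", and section 4.2.1 says "The screening examinations must be performed between 1 and 28 days before being enrolled in the study".

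For each AE, protocol section 6.8 asks for a start date, an end date, a severity and, among other items, "Outcome (resolved, ongoing, ongoing improved, ongoing worsening) and recovery date". It asks for no date of worsening and does not say whether worsening opens a new record.

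Protocol section 7.4 plans to tabulate AEs and SAEs by type, incidence, severity and relatedness, with no restriction to treatment-emergent events. SAP section 11, which lists departures from the protocol's analyses, does not mention the restriction introduced in SAP 8.1.

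**The concern.** The SAP analyses only part of what the protocol calls an AE. New events after injection are counted. Whether worsening of a screening-onset event is counted depends on how the site filled in the form.

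Pre-dose records are plausible in this population. Protocol section 5.4 allows patients to be on active anti-cancer treatment, and section 4.1.2 has abnormal physical findings entered as AEs. If one of these events becomes more severe, becomes serious or is judged drug-related after injection, but keeps its original start date, the incidence tables will not show it.

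This bears on a named secondary endpoint. Tolerability is judged partly by the absence of an increased number of SAEs compared with other peptide-based radiotracers, and the SAP's SAE summaries are restricted to treatment-emergent ones.

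The rule also runs against the SAP's approach elsewhere. Section 5.4 resolves an unclear AE onset date towards treatment-emergent. Section 8.2 compares baseline laboratory grade with the worst later grade, and section 5.2 sets the reference point as late as possible: "Baseline value for any given variable is defined as the last assessment obtained prior to the initiation of the" tracer. Symptom-type AEs have no equivalent comparison with baseline.

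**Working it through.** There is no planned figure to reproduce, because the point is about a definition. The check is to follow one event through the rules, count the outputs affected, and scale the result.

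**Step 1: follow one event.** Suppose a symptom starts in screening at grade 1, is still present at injection, and reaches grade 3 afterwards.

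- *Recorded as a new AE at the worsening.* The start date falls after injection, so SAP 8.1 counts it as a grade 3 TEAE. Protocol 6.1 permits this, since worsening is itself an AE.
- *Kept as one record with a worsening outcome code.* The start date falls before injection, so SAP 8.1 does not count it as a TEAE at any grade. The outcome list in protocol 6.8 permits this too.

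The same clinical course gives opposite results, and neither document says which record applies.

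**Step 2: count the AE outputs in SAP 8.1.**

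| Output | Limited to treatment-emergent events? |
|---|---|
| Overview rows | 8 of 9; the exception is "Deaths due to AEs" |
| SOC and PT tables (all, drug-related, serious, drug-related serious, two for dose interruption) | 6 of 6 |
| Worst-grade tables (all, drug-related) | 2 of 2 |
| Listings (SAEs, grade 3/4/5, dose interruption, hypersensitivity, death, by-subject) | None |

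A single-record event is therefore absent from every TEAE summary. It remains in whichever listings apply and, if fatal, in the deaths row.

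**Step 3: scale.** The denominator is the planned 50 patients, 10 per tumour type (SAP section 10). The documents give no rate, so let q be the assumed proportion of patients with a screening-onset AE that worsens after injection and is kept as one record.

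- Expected patients missed = 50 × q
- Chance of at least one = 1 − (1 − q)^50, taking patients as independent

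| q (assumed) | Expected missed of 50 | Chance of at least one |
|---|---|---|
| 1% | 0.5 | 39% |
| 2% | 1 | 64% |
| 5% | 2.5 | 92% |
| 10% | 5 | 99% |

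One missed patient is 1/50 = 2 percentage points overall and 1/10 = 10 points within a tumour type. These are upper values for a given table row: the tables count patients, so the loss is zero if the patient already has another event qualifying for that row.

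**The case against.** The strongest reply is that the loss is conditional and the affected group is narrow.

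- **Recording.** Protocol 6.1 makes worsening an AE in its own right. A site that enters it as a new AE dated after injection produces a TEAE under the existing definition. Protocol section 8.1 refers to e-CRF completion guidelines, which are not among the documents and may settle the matter. This stands: the protocol and SAP are silent, but it cannot be said that no instruction exists anywhere.
- **Who is affected.** A condition already present at consent that worsens after injection becomes an AE under 6.1 and is counted from its worsening. Only events that first arise between consent and injection, are ongoing at injection, worsen later and stay on one record are lost. This also stands.
- **Other outputs.** Laboratory worsening appears in the shift tables, and vital signs and ECG are summarised as change from baseline. The AE listings are complete and, with 50 patients, can be read in full. This stands for measured parameters. For symptoms, a listing does not correct an incidence table.

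A reader might infer that such events vanish from all AE reporting. They do not, given the unrestricted listings and deaths row. A reader might also infer a definite loss of 5 to 10 events, by assuming one screening AE per patient and 10% to 20% worsening (50 × 0.10 = 5; 50 × 0.20 = 10). Neither assumption has a source in the documents, and the figure also needs every worsening to stay on its original record. Comparing a 28-day pre-dose window with a 14-day post-dose window adds little: the synopsis gives screening as 28 days or less, and the schedules mark AE collection out to the optional follow-up at up to 90 days. Nor do the documents support calling worsening of existing symptoms the likeliest form of harm.

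None of this removes the mismatch between SAP 8.1 and protocol 6.1, or supplies a recording rule.

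**Conclusion.** The point holds in a limited form. The TEAE definition omits worsening, differs from the protocol's AE definition, and narrows the protocol's planned tabulation without declaring it. Whether a post-injection worsening of a screening-onset AE is counted depends on a recording convention that neither document states, so sites may differ.

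The size is unknown. The range of 0.5 to 5 patients in 50 rests on an assumed 1% to 10% of patients affected, all kept as single records. The effect is small overall but can be visible within a tumour type of 10. Safety is a descriptive secondary objective, so no hypothesis test is at risk. What is at risk is understatement of the any-TEAE, grade 3/4/5, serious and drug-related summaries. The change is worth making because it is specific and cheap.

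**What to change.** 1. In SAP 8.1, write: *TEAEs are AEs that start, or worsen in severity grade or become serious, on or after the initiation of IMP administration.* Seriousness is included because it can change without a change of grade, and the SAE summaries depend on it.
2. In the CRF completion instructions, state that post-injection worsening of a pre-dose AE is entered as a new record with its own start date and grade, or as a dated grade change on the existing record. Without a date the new definition cannot be applied. New records will not inflate the tables, because SAP 8.1 counts each patient once per SOC and PT.
3. In SAP section 11, list that AE tables are limited to TEAEs, since protocol 7.4 sets no such limit.

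The cost is one sentence in the definition, one completion instruction and one entry in section 11. Records already entered with a pre-dose start and a worsening outcome would need a site query to obtain the date. SAP section 1 allows revisions before database lock.

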#### 8.2 Safety Laboratory Parameters

Descriptive statistics will be provided at baseline and each scheduled visit for selected clinical laboratory test results (chemistry, hematology, and coagulation) and changes from baseline to each scheduled visit will be derived. The minimum post-baseline value, maximum post-baseline value, and last post-baseline value will be summarized in the same manner, where both scheduled and unscheduled post-baseline values will be considered for the derivations.

Laboratory values will be assigned toxicity grades when available using the Toxicity Grading Scale in vaccine clinical trials. Directional shifts in laboratory toxicity grades (comparing baseline grade with the worst post-baseline grade) will be analyzed using standard shift tables, presenting number and proportion of subjects and their maximum grade shift. For parameters without a toxicity grading scale, the shift table will present directional shifts from baseline to above or below the laboratory standard normal range using the maximum increase and/or decrease observed throughout the course of treatment/observation. Both scheduled and unscheduled post-baseline values will be considered when deriving the minimum/maximum/worst post-baseline assessment.

Clinical laboratory tests will also be tabulated by the number and percentage of subjects in each abnormal category (abnormal but not clinical significant, abnormal and clinical significant) for each parameter at each scheduled visit and for the worst post-baseline assessment.

Laboratory test results will also be presented graphically in terms of box plots of absolute values over time and changes from baseline over time.

All clinical laboratory data will be listed by subject using the International System of units (SI units). Values outside the normal ranges will be flagged.

#### 8.3 Vital Signs

Descriptive statistics will be provided for the vital signs measurements (systolic blood pressure, diastolic blood pressure and heart rate) and changes from baseline, if available, at each scheduled visit. The minimum post-baseline value, maximum post-baseline value, and last post-baseline value will be summarized in the same manner, where both scheduled and unscheduled post-baseline values will be included for deriving the minimum/maximum/last post-baseline value.

Vital signs results will also be presented graphically in terms of box plots of absolute values over time and changes from baseline over time.

All vital sign measurements will be listed by subject at each scheduled visit.

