# 3.3 Study Endpoints

- 3.3.1 Primary Study Endpoint
  - Number and location of tumour lesions detected by [Ga]-NeoBOMB1 overall and for each tumour type
  - Calculation of the ratio tumour/background SUV and calculation of percentage absorbed dose in tumour overall and for each tumour type.
- 3.3.2 Secondary Study Endpoints
  - Standard safety parameters (clinical monitoring, laboratory, ECG)
  - Tolerability and safety of the administration of a diagnostic dose of [Ga]-NeoBOMB1 in patients with malignancies known to overexpress GRPR as determined by absence of:
    - increased number of SAEs compared to other peptide-based radiotracers;
    - clinically relevant changes of physiological parameters (blood pressure, heart rate, ECG findings)
  - Generation of decay corrected tissue TACs from [Ga]-NeoBOMB1 PET/CT images in normal organs, tumour lesions.
  - Quantification of urinary excretion of [Ga]-NeoBOMB1
  - Calculation of half-life of [Ga]-NeoBOMB1 in blood
  - Generation of non-decay-corrected TACs from [Ga]-NeoBOMB1 PET/CT images in normal organs, tumour lesions
  - Calculation of residence times in organs and tumour lesions of [Ga]-NeoBOMB1
  - Calculation of absorbed doses and effective whole body dose of [Ga]-NeoBOMB1
  - Calculation of the SUV of each lesion
  - Number and location of tumour lesion detected by [Ga]-NeoBOMB1 in comparison with comparable standard imaging modalities such as FDG-PET

- Calculation of the [Ga]-NeoBOMB1 PET overall, positive and negative agreement on a lesion-by-lesion basis as well as on a patient basis relative to the standard imaging overall and for each tumour type
- Comparison of number of patients with tumour lesions detected and number of tumour lesions detected by [Ga]-NeoBOMB1 with cytology and/or histopathology from archival and/or recent biopsy specimens
- Calculation of the [Ga]-NeoBOMB1 PET sensitivity and specificity on a lesion-bylesion basis for all lesions with associated biopsy data, and on a patient basis relative to histopathology / cytology data

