# 7.4 Safety Analysis

Safety evaluations on the FAS will be based on the incidence, type, severity and consequences (e.g. study discontinuation) of an adverse event (AE) as well as on clinically significant changes in the patient's physical examination, ECGs, vital signs, and clinical laboratory results. ECG parameters will include heart rate (HR), RR interval, PR interval, QRS width and QTc interval. Statistical analysis includes descriptive tabulation using measures which are absolute and relative frequencies for categorical data and means, standard deviations, medians and interquartile ranges for continuous data for observed values as well as for changes from baseline in continuous parameters at each measuring time. Clinical laboratory data, ECGs and vital signs will also be presented graphically in terms of box plots of absolute values over time and changes from baseline over time. Clinical laboratory data will be summarized with respect to the normal ranges of values provided by the laboratory and with respect to predefined levels of change in these values.

All original AE/SAE terms will be coded using the Medical Dictionary for Regulatory Activities (MedDRA). Adverse events will be listed on an individual basis and will be summarized by System organ classes and preferred terms will be used in the analyses. Patients with more than one adverse event within a particular SOC and PT will be counted only once for that SOC and PT. The type and incidence of AEs/SAEs, as well as severity and relatedness to the investigational product will be tabulated.

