#### 3.2 Secondary Study Endpoints

- Standard safety parameters (clinical monitoring, laboratory, and ECG)
- Tolerability and safety of the administration of a diagnostic dose of [Ga]-NeoBOMB1 in patients with malignancies known to overexpress GRPR as determined by absence of:
  - increased number of SAEs compared to other peptide-based radiotracers;
  - clinically relevant changes of physiological parameters (blood pressure, heart rate, and ECG findings)
- Generation of decay corrected tissue time-activity curves (TACs) from [Ga]-NeoBOMB1 PET/CT images in normal organs and tumor lesions.
- Quantification of urinary excretion of [Ga]-NeoBOMB1
- Calculation of half-life of [Ga]-NeoBOMB1 in blood
- Generation of non-decay-corrected TACs from [Ga]-NeoBOMB1 PET/CT images in normal organs and tumor lesions
- Calculation of residence times in critical organs and tumor lesions of [Ga]-NeoBOMB1
- Calculation of absorbed doses in critical organs and effective whole body dose of [Ga]-NeoBOMB1
- Calculation of pharmacokinetic (PK) parameters, such as maximum concentration observed (*Cmax*), time of maximum observed drug concentration occurrence (*tmax*), area under the concentration-time curve from time zero (pre-dose) to some fixed time t [*AUC(o-t)*], AUC(0-t) divided by the dose administered [*AUC(o-t)*/D], half-life (*t*1/2), area under the concentration-time curve from time zero (pre-dose) extrapolated to infinite time [*AUC(o-tinf)*], total systemic clearance for intravenous administration (CL), the apparent volume of distribution of the parent test item in the test system (Vd)
- Number and location of tumor lesion detected by [Ga]-NeoBOMB1 in comparison with comparable standard imaging modalities such as FDG-PET
- Calculation of the [Ga]-NeoBOMB1 PET overall, positive and negative agreement on a lesion-by-lesion basis as well as on a patient basis relative to the standard imaging overall and for each tumor type
- Comparison of number of patients with tumor lesions detected by [Ga]-NeoBOMB1 with cytology and/or histopathology from archival and/or recent biopsy specimens

• Calculation of the [Ga]-NeoBOMB1 PET sensitivity and specificity on a lesion-by-lesion basis for all lesions with associated biopsy data, and on a patient basis relative to histopathology / cytology data

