#### 8.4 ECG Parameters

Electrocardiogram parameters (PR, RR, QRS, QT, QTcF, and QTcB) will be summarized using descriptive statistics for actual values and for change from baseline at each scheduled visit. The minimum post-baseline, maximum post-baseline, and last post-baseline value will be summarized in the same manner, where both scheduled and unscheduled post-baseline measurements will be considered for deriving the minimum/maximum/last post-baseline value.

Note that Frederica's and Bazett's correction to the reported QT interval, QTcF and QTcB, respectively, will be derived (in milliseconds) for all subjects and time points as follows:

QTcF (msec) = 
$$\frac{QT(msec)}{\sqrt[3]{RR(msec)/1000}}$$
; QTcB (msec) =  $\frac{QT(msec)}{\sqrt{RR(msec)/1000}}$ 

The number and percentage of subjects with elevated QTcF and QTcB during the post-baseline period will be presented for the following categories: QTcF or QTcB worsening to >450 msec, >480 msec, and >500 msec from baseline, and increase in QTcF or QTcB from baseline >30 msec and >60 msec.

Overall interpretations of ECG assessment will be tabulated by the number and percentage of subjects in each category (normal, abnormal but not clinically significant, abnormal and clinically significant, not evaluable, or unknown) at each visit and at worst post-baseline assessment.

Electrocardiogram parameters results will also be presented graphically in terms of box plots of absolute values over time and changes from baseline over time.

All ECG measurements and overall interpretation will be listed by subject.

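### The blood-pressure and heart-rate part of the tolerability endpoint has no stated criterion and no per-patient classification of the measured values in SAP 8.3; it is captured only indirectly

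*SAP*

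**What the plan says.** **The endpoint.** Tolerability is to be shown partly by the absence of certain changes. Protocol 3.3.2 names "clinically relevant changes of physiological parameters (blood pressure, heart rate, ECG findings"), and SAP 3.2 repeats it almost word for word. Neither document says what size of blood-pressure or heart-rate change is clinically relevant.

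**The basis of the safety evaluation.** Protocol 7.4 rests it on adverse events and also on "clinically significant changes in the patient's physical examination, ECGs, vital signs, and clinical laboratory results". It then specifies descriptive tabulation of values and changes, with box plots. It asks for predefined levels of change for laboratory data only.

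**The vital-sign analysis.** SAP 8.3 states: "Descriptive statistics will be provided for the vital signs measurements (systolic blood pressure, diastolic blood pressure and heart rate) and changes from baseline". Minimum, maximum and last post-baseline values are summarised too, unscheduled readings included, and box plots are drawn. Finally, "All vital sign measurements will be listed by subject at each scheduled visit". There is no threshold, grade, shift table or clinical-significance category.

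**The neighbouring sections.** For laboratory tests, SAP 8.2 says "Laboratory values will be assigned toxicity grades when available using the Toxicity Grading Scale in vaccine clinical trials", and adds shift tables and counts by clinical significance. For ECG, SAP 8.4 counts patients by QTc category and by overall interpretation, including "abnormal but not clinically significant, abnormal and clinically significant".

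**The concern.** An endpoint worded as the absence of something in individual patients needs a decision, patient by patient, on whether it occurred. For ECG, which stands in the same endpoint sentence, the SAP arranges that decision. For measured blood pressure and heart rate it does not.

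A short-lived haemodynamic reaction in a few patients after the injection is what this component should be able to show. Summaries of the whole group's distribution are insensitive to it. A listing allows a hand count, but with a criterion chosen after the data are seen. The report could then state that no clinically relevant changes occurred without any prespecified output that supports or contradicts the statement.

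**Working it through.** **1. Where is a patient classified?**

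| Component | Measured values classified per patient? | Place |
|---|---|---|
| Laboratory tests | Yes: toxicity grade, shift from baseline, clinical significance | SAP 8.2 |
| ECG | Yes: QTc categories, overall interpretation | SAP 8.4 |
| Blood pressure | No | SAP 8.3 |
| Heart rate | No; partly reflected in ECG interpretation | SAP 8.3, 8.4 |

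**2. What reaches the adverse-event tables?** Protocol 6.1 counts signs that emerge or worsen from baseline as adverse events. SAP 8.1 grades all adverse events on the protocol's toxicity scale and counts patients by worst grade. The scale has rows for tachycardia, bradycardia, systolic and diastolic hypertension, and systolic hypotension. So a vital-sign change that is reported is graded and counted. Whether it is reported is left to the investigator: Protocol 4.1.2 turns abnormal physical-examination findings into adverse events, but Protocol 4.1.3 on vital signs has no such rule.

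**3. What can the planned summaries show?** The plan gives no figure on this point, so the following is illustrative. Assumptions, not in the documents: 3 of the 50 planned patients have a 30 mmHg systolic fall at one time point, and the SD of change is 10 to 15 mmHg.

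- Shift in mean change = −30 × 3/50 = −1.8 mmHg.
- Standard error = 10/√50 = 1.41 to 15/√50 = 2.12 mmHg.
- The shift is 1.8/2.12 = 0.85 to 1.8/1.41 = 1.27 standard errors.
- The minimum shows the most extreme patient, not how many there were.

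**4. What would a count show?** The plan's only worked precision figure, 66.4% to 92.7% for 25/30 (Protocol 7.1, SAP 10), reproduces with the Wilson score method. The exact (Clopper-Pearson) interval is 65.3% to 94.4%. Exact 95% intervals for counts here:

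- 0/50: upper limit 1 − 0.025^(1/50) = 7.1% (Wilson also 7.1%)
- 1/50: 0.1% to 10.6%
- 3/50 = 6.0%: 1.3% to 16.5%
- 0/10, one tumour type: upper limit 1 − 0.025^(1/10) = 30.8%

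**5. How does the protocol's scale behave on measured values?** Its cut-offs are absolute. Systolic hypotension starts at 89 mmHg and systolic hypertension at 141 mmHg.

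- 130 to 100 mmHg: a 30 mmHg fall, ungraded before and after. A fall of that size is graded only from a baseline of 119 mmHg or lower (119 − 30 = 89).
- 140 to 141 mmHg: a 1 mmHg rise, grade 0 to grade 1.
- 140 to 151 mmHg: an 11 mmHg rise, grade 0 to grade 2.
- Above 155 mmHg at baseline (grade 3): no measured rise can worsen the grade, because grade 4 is defined by an emergency-room visit or hospitalisation.
- Diastolic pressure has hypertension grades only, so a diastolic fall is not graded.

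A shift table on this scale therefore gives a prespecified count, but not a complete reading of clinical relevance.

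**The case against.** The best defence is that the trial is descriptive, has 50 patients, and already has a route for such events. An untoward blood-pressure or heart-rate change is an adverse event under Protocol 6.1, vital signs are monitored during the injection (Protocol 4.1.6), and SAP 8.1 counts patients by grade, term and relatedness. Every vital-sign value is listed, and each patient's extremes are derived. Heart rate also appears through the RR interval and the ECG interpretation.

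Much of this stands, and it rules out three stronger readings that a reader might infer.

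- *That this part of the endpoint is not assessed at all.* It is assessed, indirectly, whenever a change is reported as an adverse event.
- *That SAP 8.3 is an undeclared departure that belonged in SAP 11.* Protocol 7.4 itself prescribes descriptive tabulation and box plots for vital signs, and SAP 8.3 carries that out.
- *That physical examination has the same gap because SAP 8.5 only lists it.* Protocol 4.1.2 sends abnormal findings to the adverse-event tables.

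The defence does not supply a criterion. The adverse-event route depends on each investigator's unstated threshold, at several centres and open label, and no section names SAP 8.1 as the analysis of this component. Protocol 6.1 lists abnormal laboratory tests as adverse events, yet SAP 8.2 still classifies the measured laboratory values separately. Adverse-event capture was thus not the only route provided there.

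**Conclusion.** The point holds as a limited gap in specification. The blood-pressure and heart-rate part of the tolerability endpoint has no stated criterion and no per-patient classification of measured values. It is covered only through reported adverse events and, for heart rate, ECG interpretation, with no rule linking a vital-sign change to an adverse event.

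This conclusion rests on the text alone. The size of the insensitivity (a mean shift of 1.8 mmHg, or 0.85 to 1.27 standard errors) depends on the assumed number of patients, fall and SD. The interval limits depend only on 50 patients being evaluable. Even a clean result would be modest evidence: 0/50 is compatible with a true rate of up to 7.1%.

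The primary analysis is not affected. The change is worth making because it is cheap and lets a stated secondary endpoint be answered by a rule fixed in advance.

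**What to change.** SAP section 1 allows revision before database lock. By then:

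1. Add to SAP 8.3 the table type used in 8.2: baseline grade against worst post-dose Day 1 grade, and against worst post-baseline grade. Use the vital-sign rows of the protocol's toxicity scale for systolic pressure, diastolic pressure and heart rate, with upward and downward shifts shown separately where the scale has both.
2. Report the number, percentage and exact 95% CI of patients who worsen. Show the full table beside the count, so that one-grade shifts can be told from larger ones.
3. Keep the change-from-baseline summaries next to it, because the scale does not flag large falls that end above the hypotension range.
4. Name these outputs, together with the SAP 8.1 tables, as the analysis of this endpoint component.
5. If the sponsor wants a further criterion for clinical relevance, state it before lock. That choice is clinical, and none is proposed here.

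The cost is one or two tables from data already collected. Some shifts will be measurement noise. Protocol 4.1.3 gives three post-dose Day 1 readings in the dosimetry group and one in the non-dosimetry group, so a worst-of-day count should also be shown by group.
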